## **10. BG00012 DESCRIPTION AND ALLOCATION**

BG00012 is a drug product formulated as enteric-coated microtablets in gelatin capsules (blue and white) for oral administration. Each capsule contains 120 mg DMF.

Excipients for the manufacturing of the enteric-coated microtablets include microcrystalline cellulose, croscarmellose sodium, talc, colloidal anhydrous silica (colloidal silicon dioxide), magnesium stearate, triethyl citrate, methacrylic acid-methyl methacrylate copolymer, methacrylic acid-ethyl acrylate copolymer, simeticone, sodium laurilsulfate, and polysorbate 80. Excipients for the manufacturing of the capsule shell include gelatin, titanium dioxide, and indigotine.

The label will include conditions for storage, lot number, and other pertinent information such as manufacturer, batch/lot number, and caution statement. Depending on country requirements, the Investigator's name may also appear on the label.

BG00012 is to be stored at 15 to 25°C in a secure location, preferably a monitored, locked cabinet. Accountability for BG00012 is the responsibility of the Investigator. More details concerning this responsibility are included in Section 10.2.

Study site staff should refer to the Directions for Handling and Administration (DHA) located in the Study Reference Guide for specific instructions on the handling and administration of BG00012. The individual dispensing BG00012 should first carefully review the instructions provided in the DHA, which supersedes all other references (e.g., Investigator's Brochure or commercial product prescribing information).

BG00012 must only be dispensed by qualified study staff and is to be dispensed only to subjects enrolled in this study. Do not use BG00012 after the expiration date unless a written notification of an expiration date extension is provided by Biogen. Once BG00012 is dispensed to a subject, it can only be taken by that subject.

### **10.1. BG00012 Packaging**

The qualified study staff will dispense to subjects at least a 4-week supply of BG00012 at the Baseline Visit and at each subsequent study visit (excluding the End of Study Visit, Premature Study Treatment Withdrawal Visit, and the Unscheduled Relapse Assessment Visit).

BG00012 is provided in drug wallets identified by kit numbers supplied from an Interactive Voice and Web Response System (IXRS) at specific timepoints during the study.

During the dose-blind phase, BG00012 kits included 6 capsules per day (2 capsules each for the morning, noon, and evening doses). During the open-label treatment, the noon dose is eliminated, and the new kit will include 4 capsules per day (2 capsules each for the morning and evening doses).

### **10.2. BG00012 Accountability**

The study site must maintain accurate records demonstrating dates and amount of BG00012 received, to whom dispensed (subject-by-subject accounting), amount returned by subject, and

CONFIDENTIAL

The information contained herein may not be used, disclosed, or published without the written consent of Biogen MA Inc.

accounts of any BG00012 accidentally or deliberately destroyed. The date (Study Visit/Week) that each subject switched to open-label treatment with 240 mg BID should also be recorded in the CRF.

Unless otherwise notified, all capsules both used and unused, must be saved for BG00012 accountability. At the end of the study, reconciliation must be made between the amount of BG00012 supplied, dispensed, and subsequently destroyed or returned to Biogen. A written explanation will be provided for any discrepancies.

The Investigator must return all unused capsules of BG00012 as instructed by Biogen. If any BG00012 supplies are to be destroyed at the site, the institution/Principal Investigator(s) must obtain prior approval by Biogen. After such destruction, the institution/Principal Investigator(s) must notify Biogen, in writing, of the method of destruction, the date of destruction, and the location of destruction.

CONFIDENTIAL

The information contained herein may not be used, disclosed, or published without the written consent of  
Biogen MA Inc.

## 11. TREATMENT

### 11.1. Treatment Schedule

At enrollment into the study, all subjects received either:

- BG00012 240 mg BID (2 capsules [120 mg each] twice a day and 2 placebo capsules once a day).

OR

- BG00012 240 mg TID (2 capsules [120 mg each] 3 times a day).

Subjects randomized to BG00012 in Study 109MS301 or 109MS302 continued on the same BG00012 dose in this extension study.

Subjects randomized to placebo in Study 109MS301 or 109MS302 or to GA in Study 109MS302 were randomized to BG00012 240 mg BID or 240 mg TID at a 1:1 ratio in this extension study.

Subjects who switched to an alternate approved MS therapy in Study 109MS301 or 109MS302 were randomized in this extension study as outlined above according to their original treatment group in Study 109MS301 or 109MS302.

All subjects continuing in the extension study are currently receiving the currently marketed dose of BG00012 240 mg BID (2 capsules [120 mg each] BID). Subjects randomized to BG00012 240 mg TID were switched to BID dosing (2 capsules [120 mg each] BID) following BG00012 approval.

Subjects who complete BG00012 treatment or permanently discontinue BG00012 for any reason and who have a lymphocyte count <LLN should not be withdrawn from the study. These subjects will be followed according to Section 11.3.

### 11.2. Modification of Treatment Schedule

#### 11.2.1. Abnormal Laboratory Values: Dosing Interruption and Management

BG00012 must be temporarily withheld when any of the following laboratory values meet the criteria defined in [Table 1](#). Subjects are required to have additional evaluation when any of the following laboratory values meet the threshold limits defined in [Table 2](#).

CONFIDENTIAL

The information contained herein may not be used, disclosed, or published without the written consent of Biogen MA Inc.

**Table 1: Laboratory Criteria Requiring Withholding or Permanent Discontinuation of BG00012**

Laboratory Parameter	Laboratory Result	Required Action
AST or ALT	>3×ULN	The Investigator should repeat the test as soon as possible. If re-test value confirms AST or ALT >3×ULN, BG00012 must be withheld. If the value remains >3×ULN for ≥4 weeks after discontinuation of BG00012, then the subject must permanently discontinue BG00012.
Lymphocyte counts	<500/mm 	See Table 3 .

ALT = alanine transaminase; AST = aspartate transaminase; ULN = upper limit of normal.

While dosing is withheld, subjects will continue tests and assessments according to the schedule defined in the protocol (Section 4), and may also undergo additional assessments to evaluate the laboratory abnormality as per the Investigator’s standard practice. Subjects who have abnormal laboratory results other than described in [Table 1](#) must repeat the tests within 2 weeks (repeat tests will be run at the central laboratory). Abnormal laboratory results confirmed on repeat tests should be managed per the Investigator’s standard practice.

Subjects who subsequently develop the same abnormal laboratory value at any other time during the study must permanently discontinue dosing with BG00012, i.e., only 1 dosing interruption is allowed for each subject for the same laboratory abnormality (see [Table 1](#)). However, subjects who subsequently experience a different laboratory abnormality can have BG00012 withheld again, allowing 2 dosing interruptions for each subject. Any subject who experiences abnormal laboratory results that require temporary withholding as defined in [Table 1](#) on a third occasion must permanently discontinue dosing.

Subjects who complete BG00012 or permanently discontinue BG00012 for any reason and who have a lymphocyte count <LLN will be followed according to [Section 11.3](#).

**Table 2: Laboratory Analyses That Require Additional Evaluation**

Laboratory Parameter	Laboratory Result	Required Action
Urinalysis	Urinary casts (other than hyaline casts)	Repeat test 2 weeks later; if the abnormality persists on re-testing, the subject should be followed as per standard of care.
Urinalysis	Glycosuria (trace or greater)	If occurring in the setting of normal serum glucose, repeat test 2 weeks later; if the abnormality persists on re-testing, the subject should be followed as per standard of care.

CONFIDENTIAL

The information contained herein may not be used, disclosed, or published without the written consent of Biogen MA Inc.

Laboratory Parameter	Laboratory Result	Required Action
Urinalysis	Proteinuria 1+	Subjects who demonstrate 1+ proteinuria (and do not have a documented history of benign proteinuria) should be re-tested within 2 weeks of initial abnormal finding. If the abnormality persists on re-testing, the subject should be followed as per standard of care.

### 11.2.2. Dosage Reductions

Dosage reduction will be allowed only for subjects who are unable to tolerate BG00012 *due to flushing and/or GI disturbances* (dosage reductions will not be allowed for abnormal laboratory values; for management of abnormal laboratory values, refer to Section 11.2.1). Subjects who do not tolerate BG00012 will reduce their dosage by taking one 120-mg capsule BID for 4 weeks. After 4 weeks at the reduced dosage, subjects will resume taking the full dose of 240 mg (two 120 mg capsules) BID. If the subject is still unable to tolerate BG00012, the subject must discontinue BG00012 and be withdrawn from the study as described in Section 11.2.

### 11.2.3. Resumption of BG00012 Dosing

Subjects who have temporarily withheld BG00012 due to lymphopenia may resume BG00012 according to Section 11.3.

Subjects who are allowed to resume BG00012 dosing following a 2- to 4-week interruption due to *flushing and/or GI disturbances* will restart dosing at a reduced dosage for 1 week. Subjects will take one 120 mg capsule BID for 1 week. After 1 week at the reduced dose, subjects will resume taking two 120 mg capsules BID.

## 11.3. Monitoring and Management for Subjects with Abnormal Lymphocyte Count

Subjects who have a lymphocyte count  $<500/\text{mm}^3$  at any time should be monitored and managed according to Table 3.

All subjects who complete BG00012 treatment or permanently discontinue BG00012 for any reason other than those specified in Table 3, and who have a lymphocyte count  $<LLN$ , will be monitored every 12 weeks until their lymphocyte count is  $\geq LLN$  OR for 48 weeks after their last dose, whichever is earlier.

CONFIDENTIAL

The information contained herein may not be used, disclosed, or published without the written consent of Biogen MA Inc.

**Table 3: Lymphocyte Monitoring and Management for Subjects Who Have a Lymphocyte Count  $<500/\text{mm}^3$**

For subjects who have a lymphocyte count  $<500/\text{mm}^3$ , the Investigator should repeat the test as soon as possible. If re-test confirms that the lymphocyte count remains  $<500/\text{mm}^3$ , lymphocyte counts should be monitored every 4 weeks while on BG00012.

If subject has lymphocyte counts  $<500/\text{mm}^3$  for  $\geq 24$  weeks, subject meets the **Temporary Withholding Rule** and BG00012 will be temporarily withheld. If the Temporary Withholding Rule is not met, the subject will be monitored every 12 weeks.

CONFIDENTIAL

The information contained herein may not be used, disclosed, or published without the written consent of Biogen MA Inc.

Lymphocyte Monitoring for Subjects Meeting the Temporary Withholding Rule	Management for Subjects Meeting the Temporary Withholding Rule

The subject will be monitored every 4 weeks for 24 weeks, then every 12 weeks until the lymphocyte count is <math>\geq</math>LLN OR for 96 weeks after their last dose, whichever is earlier. However, if a subject reaches the end of study and their lymphocyte count remains <math><</math>LLN, the subject will be monitored every 12 weeks until the lymphocyte count is <math>\geq</math>LLN OR for 48 weeks after their last dose, whichever is earlier.
	
 
• If lymphocyte count remains <math><500/\text{mm}^3</math> for 24 weeks after temporary withdrawal, BG00012 must be permanently discontinued.
 
• If lymphocyte count is between <math>\geq 500/\text{mm}^3</math> and <math>\leq 800/\text{mm}^3</math>, then BG00012 will continue to be temporarily withheld.
 
• If lymphocyte count recovers to <math>>800/\text{mm}^3</math> (confirmed by 2 tests, at least 4 weeks apart), the physician/patient has the option to restart BG00012. If, upon resumption of BG00012, the lymphocyte count is <math><500/\text{mm}^3</math> on 1 occasion (confirmed by repeat testing), then BG00012 must be permanently discontinued.
 
• Alternative disease-modifying treatmenta may be considered, at the discretion of the treating physician as per standard of care. Subjects treated with alternative disease-modifying treatment will not have the option to restart BG00012.
 

AE = adverse event; CRF = case report form; LLN = lower limit of normal.

a The use of concomitant therapies as defined above must be recorded on the subject's CRF, according to instructions for CRF completion. AEs related to administration of these therapies or procedures must be documented on the appropriate CRF.

Optional hematology consult and/or bone marrow biopsy may be considered for subjects meeting the Temporary Withholding Rule at the discretion of the Investigator. Earlier hematology consult and/or bone marrow biopsy may be considered in consultation with the Medical Monitor.

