### 4.3. Study Activities (Years 4 Through 8 Treatment Visits)

Year	Year 4				Year 5				Year 6				Year 7				Year 8			
Visit	17	18	19	20	21	22	23	24	25	26	27	28	29	30	31	32	33	34	35	36 
Study Week (±7 days)	156	168	180	192	204	216	228	240	252	264	276	288	300	312	324	336	348	360	372	384
Tests and Assessments																				
Physical Examination		X		X		X		X		X		X		X		X		X		X
Vital Signs	X	X	X	X	X	X	X	X	X	X	X	X	X	X	X	X	X	X	X	X
Hematology	See Section 4.5																			
Blood Chemistry		X		X		X		X		X		X		X		X		X		X
Urine Pregnancy Test 		X		X		X		X		X		X		X		X		X		X
Urinalysis		X 		X 		X 		X 		X 		X 		X 		X 		X 		X 
Brain MRI  Scan ± Gd 	Scheduled MRI scans were performed in protocol versions 1 through 6.																			
EDSS		X		X		X		X		X		X		X		X		X		X
Visual Function Test		X		X		X		X		X		X		X		X		X		X
SF-36 and EQ-5D				X				X				X				X				X
Dispense Study Treatment (BG00012) 	X	X	X	X	X	X	X	X	X	X	X	X	X	X	X	X	X	X	X	X
Concomitant Therapy and Procedures Recording	Monitor and record throughout the study as per Section 11.6																			
AE/SAE Reporting	Monitor and record throughout the study as per Section 15																			

AE = adverse event; CRF = case report form; [redacted]; EDSS = Expanded Disability Status Scale; EQ-5D = EuroQol EQ-5D Health Survey; Gd = gadolinium; MRI = magnetic resonance imaging; [redacted]; SAE = serious adverse event; SF-36 = Short-form 36 Health Survey.

- For subjects who have already completed Visit 36 (or beyond), an End of Study Visit should be completed 4 weeks after their next visit (scheduled or unscheduled), regardless of further need to monitor lymphocytes on study.
- Tests and assessments must be completed prior to BG00012 distribution.
- For women of childbearing potential. Results must be known prior to BG00012 distribution.
- If urinalysis is abnormal, see Section 11.2.
- Only in subjects who had MRI scans as part of Studies 109MS301 and 109MS302 and in 109MS303 up through and including Amendment 6.

CONFIDENTIAL

The information contained herein may not be used, disclosed, or published without the written consent of Biogen MA Inc.

6. MRI must not be performed within 30 days of receiving a course of steroids.

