**4.5. Study Activities (Hematology [REDACTED] Analysis: Year 4 Through End of Treatment Visits)**

Tests and Assessments	Subjects With Lymphocyte Count $\geq$ LLN	Subjects With Lymphocyte Count $<$ LLN to $\geq$ 500/mm 	Subjects With Lymphocyte Count $<$ 500/mm 
Hematology	Every 12 weeks	Every 12 weeks	Every 4 or 12 weeks per Table 3
[REDACTED]			
Bone Marrow Biopsy (optional)	Not applicable	Not applicable	Optional procedure 

[REDACTED] LLN = lower limit of normal; [REDACTED]

6. See Section [11.3](#) for further details.

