3.5 Study Activities (Hematology and Analysis: Year 4 Through End of Treatment Visits)

Tests and Assessments	Subjects With Lymphocyte Count ≥LLN	Subjects With Lymphocyte Count <lln mm3</lln>	Subjects With Lymphocyte Count <500/mm ³
Hematology	Every 12 weeks	Every 12 weeks	Every 4 or 12 weeks per Protocol Table 3
Bone Marrow Biopsy (optional)	Not applicable	Not applicable	Optional procedure ⁶
LLN = lower l	mit of normal;		

6. See Protocol Section 11.3 for further details

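### Protocol Table 3 contradicts itself: a subject on BG00012 with a confirmed lymphocyte count below 500/mm³ for under 24 weeks is assigned both 4-weekly and 12-weekly monitoring

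*Protocol*

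**What the plan says.** Protocol Section 11.3 sends to Table 3 every subject whose count falls below 500/mm³: such a subject "at any time should be monitored and managed according to Table 3". Table 3 then says, in order:

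- After a first low count, "the Investigator should repeat the test as soon as possible".
- If the re-test confirms the low count, "lymphocyte counts should be monitored every 4 weeks while on BG00012".
- Counts that stay below 500/mm³ for 24 weeks or more trigger the Temporary Withholding Rule, under which dosing is suspended.
- The paragraph on that rule closes with a further instruction: "If the Temporary Withholding Rule is not met, the subject will be monitored every 12 weeks".

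The schedule of activities does not settle the interval. For subjects below 500/mm³, the hematology entry in Protocol Section 4.5 reads "Every 4 or 12 weeks per" Table 3, and SAP Section 3.5 reads "Every 4 or 12 weeks per Protocol Table 3". Both return the reader to the table.

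**The concern.** The 4-week sentence covers anyone with a confirmed low count who is still on drug, and it has no earlier end point than leaving drug. The 12-week sentence covers anyone for whom the Temporary Withholding Rule is not met. That rule needs at least 24 weeks of low counts, so during the first 24 weeks of a confirmed low count it is by definition not met. Such a subject falls under both sentences.

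The withholding rule works only through serial counts. Two sites could follow Table 3 in good faith and sample at different intervals, and the one sampling less often may establish the 24-week criterion later, with the subject still on drug. A monitor could not say which site had departed from the protocol, although SAP Section 6.3.3 calls for deviations to be listed.

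For scale, and as background only, the amendment history reports that 2% of subjects across the BG00012 clinical studies had counts below 0.5 × 10⁹/L for at least six months. Applied to the 1738 subjects in SAP Section 2.1, that is 0.02 × 1738 ≈ 35 people. This illustrates the order of magnitude; it is not a count for this study.

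**Working it through.** The documents give no figure for recognition delay, so there is none to reproduce. The check has a textual part and a visit-grid part.

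**Text, by subject state**

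- Confirmed below 500/mm³, under 24 weeks, on drug: the 4-week sentence applies (confirmed, on drug), and so does the 12-week sentence (rule not met). Two intervals.
- Re-test does not confirm, or count has recovered: only the 12-week sentence clearly applies.
- Rule met, drug withheld: the separate follow-up column of Table 3 applies (4-weekly for 24 weeks, then 12-weekly).

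Only the first state is in conflict.

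**Inputs for the arithmetic**

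- Intervals g = 4 or 12 weeks, and a criterion of 24 weeks: Table 3.
- Visit window of ±7 days around the 12-weekly visits: Protocol Section 4.3. I assume the same window for 4-weekly visits.
- Clock start: not stated. It could be the first low count or the re-test, and the re-test has no fixed date. I therefore vary the offset r, in weeks, between the last scheduled visit and the clock start.
- Both series are assumed to stay on the scheduled-visit grid. Anchoring either one at the re-test would change the figures.

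**Number of counts in 24 weeks.** 24/4 = 6 against 24/12 = 2.

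**Delay beyond Week 24, visits exactly on schedule.** Delay = g × ceil((24 + r)/g) − r − 24.

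| r (weeks) | 4-weekly delay | 12-weekly delay | Extra |
|---|---|---|---|
| 0 | 0 | 0 | 0 |
| 1 | 28 − 25 = 3 | 36 − 25 = 11 | 8 |
| 2 | 28 − 26 = 2 | 36 − 26 = 10 | 8 |
| 3 | 28 − 27 = 1 | 36 − 27 = 9 | 8 |
| 4 | 28 − 28 = 0 | 36 − 28 = 8 | 8 |
| 6 | 32 − 30 = 2 | 36 − 30 = 6 | 4 |
| 8 | 32 − 32 = 0 | 36 − 32 = 4 | 4 |

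The extra delay is 8 weeks for offsets above 0 and up to 4, 4 weeks for offsets above 4 and up to 8, and 0 beyond that up to 12. If the clock start is uniform between two 12-weekly visits (assumed), the mean extra delay is (8 + 4 + 0)/3 = 4 weeks (mean delays 2 and 6 weeks), and it is at least 4 weeks in two thirds of cases.

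**Visit-window drift, clock at a scheduled low count.** Take both visit days as uniform and independent on −7 to +7 (15 values) and require a full 168 days. The visit near Week 24 falls short with probability (1 − 1/15)/2 = 7/15 ≈ 47%. The next count is then near Week 28 or Week 36, so 36 − 28 = 8 weeks apart. A simulation of 400,000 draws gave mean recognition at 26.0 against 29.8 weeks.

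The strict 168-day cutoff is also an assumption. The shortest gap the two windows allow is 168 − 14 = 154 days, which SAP Section 6.4.4 accepts for 24-week EDSS confirmation. If a like tolerance applied to lymphocytes, the drift case would disappear. The documents state none.

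**The case against.** The strongest reply is that the sentences are sequential: 4-weekly while the confirmed low count lasts, 12-weekly if the episode ends without meeting the rule. The rival reading does badly. If the 12-week sentence governed everyone short of 24 weeks, subjects before that point would be 12-weekly and those beyond it would be off drug, leaving the 4-week sentence with almost nobody. Section 4.5 also gives 12 weeks to subjects at or above 500/mm³, which suits a recovered subject. A superseded version of the lymphocyte section likewise placed 4-weekly monitoring before withholding.

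This makes the sequential reading plausible, perhaps the intended one. But no current passage limits the 12-week sentence to unconfirmed or recovered counts, and superseded text cannot repair current wording. The combined entry in Section 4.5 fits either reading, and could also reflect the follow-up schedule after withholding.

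Two further objections stand. First, a reader might infer that 12-weekly monitoring always delays recognition by 8 weeks. It does not: 24 is a multiple of both intervals, so an aligned schedule gives no delay.

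Second, a reader might infer that the primary safety analysis loses lymphocyte data. The documents do not support that. No lymphocyte analysis is designated primary; SAP Section 6.5.1 defines the primary safety analyses by population, grouping and dataset. SAP Section 6.5.6 centres on the period after interruption or discontinuation. For by-visit summaries, SAP Section 6.3.8 keeps one observation per visit window, so on the 12-weekly grid most extra 4-weekly counts would not enter. Worst-value summaries (SAP Section 6.5.4) could be touched, but that is a minor effect.

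**Conclusion.** The point holds as an internal contradiction in the current text of Table 3, confined to subjects on drug with a confirmed count below 500/mm³ for under 24 weeks. Its consequence is possible rather than certain. The contrast in follow-up counts rests on the two stated intervals alone. The size of any delay rests on assumptions about clock start, visit timing, the anchoring of the visit grid and a strict 24-week cutoff; under those examined here it runs from none to about 8 weeks. The matter is one of site conduct and of applying a safety rule consistently, not of bias in a designated analysis. It merits correction because the rule depends on serial counts and the correction is cheap.

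**What to change.** The sponsor should reconcile the two sentences in Protocol Table 3 so that each state has exactly one stated interval: confirmed below 500/mm³ for under 24 weeks; unconfirmed or recovered; rule met. Table 3 should also say whether the 24-week clock starts at the first low count or at the confirming re-test. Which interval applies to which state is for the sponsor to decide.

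Protocol Section 4.5 and SAP Section 3.5 then follow by reference and need no separate rule. The cost is clarifying wording in one table and a memo to sites.
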